4.2.2. Subject Withdrawal Criteria

All subjects are free to withdraw from participation in this trial at any time, for any reason, specified or unspecified, and without penalty or loss of benefits to which the subject is otherwise entitled.

In addition, subjects may be withdrawn from the trial for any of, but not limited to, the following reasons:

- Protocol violation (non-compliance with medication or evaluation schedule with impact on subject risk-to-benefit or on protocol integrity)
- Serious illness that results in subject's inability to receive therapy or be evaluated per protocol requirements

- Discretion of Principal Investigator
- Voluntary withdrawal by subject or parent or legal guardian (efforts should be made to conduct a termination study visit)
- Death
- Sponsor terminates the study

Reason for withdrawal and the date of withdrawal should be documented. Medexus should be notified within 24 hours of all study withdrawals and every effort should be made to conduct an early termination evaluation.

The sponsor reserves the right to terminate the study or withdraw any subject from the study for any reason at any time.

If a subject is withdrawn from the trial, they will not be re-entered into the trial for any reason.

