2. DEFINITIONS

Annualized Bleeding Rate (ABR) is defined as number of bleeding episodes per year.

An adverse event (AE) is defined as any untoward, undesirable, or unintended medical occurrence in a clinical trial subject administered APVO101 which does not necessarily have a causal relationship with APVO101. For purposes of this clinical trial, an AE can therefore be any unfavorable and unintended sign (e.g., including an abnormal laboratory finding), symptom, or disease temporally associated with the use of APVO101, whether or not related to the product.

Examples of **major surgical procedures** (surgery) include synovectomy, knee or hip replacement, total tooth extraction, tonsillectomy and/or adenoidectomy, surgery for intracranial hemorrhage, radial head excision, arthrodesis, ankle surgery, abdominal surgery, herniorrhaphy, or surgery for major muscle bleed management.

A **bleeding episode** will be defined as a unique entry in the subject bleeding diary. In the event that a bleeding episode occurring at multiple locations is recorded as multiple entries in the bleeding diary, these will be considered as one bleeding episode provided that all entries have the same start date.

Bleeding episodes severity:

- Minor: e.g., uncomplicated hemarthroses and superficial muscle (except iliopsoas) with no neurovascular compromise, other soft tissue bleeds
- Moderate: e.g., hemarthrosis of longer duration, recurrent hemarthrosis, mucous membranes, deep lacerations, hematuria
- Major or life-threatening: e.g., iliopsoas, deep muscle with neurovascular injury, substantial blood loss, central nervous system, pharyngeal, retropharyngeal, retroperitoneal.

Compliance will be calculated for each subject based on actual and planned number of APVO101 doses in the study. The actual number of doses will be counted from the first dose in the treatment phase up to and including the last APVO101 dose date on study. The number of infusions expected will be calculated for each subject based on their prescribed dosing regimen. If a patient received APVO101 dose twice weekly during whole study compliance will be calculated as following:

Compliance % = $100\% * [\text{number of infusions recorded in the subject diary} / (\text{date of last dose for prophylaxis} - \text{date of first dose}) * 2/7]$

if a patient first received APVO dose twice weekly and then dose frequency was adjusted to once weekly per investigator discretion, compliance will be calculated as following:

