Compliance % = $100\% [\text{number of infusions recorded in the subject diary} / (A + B)]$, where $A = [2 * (\text{date of last dose when patient was on 'twice weekly' frequency} - \text{date of first dose})] / 7$

$B = (\text{date of last dose when patient was on 'once weekly' frequency} - \text{date of first dose when patient was on 'once weekly' frequency}) / 7$

If patient dose-frequency was changed more than once, compliance will be calculated similar to the above but taking into account all periods of different dose frequencies in the denominator.

The following **measures of exposure** will be presented for the study:

Parameter	Description
Exposure Day (ED)	APVO101 exposure/infusion. ED will be calculated as the total number of APVO101 infusions during all phases of the study: Pharmacokinetic (PK) [1], Treatment, and Continuation phases, including surgery if applicable. If a subject receives more than one infusion in a single day, all infusions on that day will count as one ED.
Average Exposure per exposure day (IU)	Average APVO101 dose (IU): Sum of all dosages received by a subject (excluding PK doses and dosing during surgery), divided by number of exposure days (excluding PK and surgery)
Average Exposure per exposure day (IU/kg)	Similar to above but for dose in IU/kg
Total Exposure (IU) – PK phase	Planned PK dose IU [2]
Total Exposure (IU/kg) – PK phase	Planned PK dose IU/kg [2]
Total Exposure (IU) –	N/A, no surgeries in the study at the moment of the Statistical Analysis

Surgeries	Plan (SAP) update [3]
Total Exposure (IU/kg) – Surgeries	N/A, no surgeries in the study at the moment of the SAP update [3]
Total Exposure (IU) – All Phases combined including surgeries	Sum of all doses (IU) during the study (PK [1], Treatment and Continuation phases, including surgery if applicable).
Total Exposure (IU/kg) – All Phases combined including surgeries	Similar above but for dose in (IU/kg)

[1] including additional PK during Treatment/Continuation phases

[2] PK during Treatment/Continuation phases should not be included

[3] if surgeries occur in the study by the time of database lock, exposure during surgeries will be derived similar to other total exposure parameters, i.e., as sum of all doses in IU or IU/kg associated with surgery.

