10.8.1 EXPOSURE TO STUDY TREATMENT AND COMPLIANCE

Exposure and compliance parameters will be summarized descriptively. Parameters to be summarized are specified in section 2.

In addition, number and percentage of subjects who fall under the following categories (not mutually exclusive) of treatment exposure will be presented:

- Subjects with ≥ 50 ED
- Subjects with ≥ 100 ED
- Subjects with ≥ 150 ED
- Subjects with ≥ 200 ED

Number of surgeries overall and per subject, number of infusions due to surgeries overall and per surgery, and total dose administered per surgery will be calculated by treatment regimen (bolus vs. continuous infusion); subjects may receive both bolus and continuous infusions and, in such cases, will be included in the summaries for both treatment regimens. For subjects treated with bolus infusion, the number of bolus infusions, average APVO101 dose (IU/kg), and total APVO101 exposure (IU) will be presented by surgery visit (pre-surgery and post-surgery) and overall. For subjects treated with continuous infusion, the average APVO101 dose (IU/kg/hr) and total APVO101 exposure (IU) will be presented.

Compliance derivation algorithm is provided in section 2. Compliance will be summarized as continuous variable as well as categorized into $\geq 80\%$, $< 80\%$. Reasons for dose/frequency modifications will also be tabulated.

Summaries described in this section will be done separately for Treatment/Continuation Phases combined, surgeries and overall, except for compliance and reasons for dose/frequency modifications which will be presented for all study duration.

A by-subject listing with the treatment administration data will be presented. In addition, a listing of all derived parameters will be produced, and it will include total value of exposure (IU) and exposure days per study.

Dose regimen data together with reasons for changes in dose regimen will be listed.

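### Compliance expects no infusions after the last prophylaxis dose taken, so a child who permanently stops prophylaxis before leaving the study is scored too high

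*SAP*

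**What the plan says.** SAP section 2 states the principle: "Compliance will be calculated for each subject based on actual and planned number of APVO101 doses in the study". It adds: "The number of infusions expected will be calculated for each subject based on their prescribed dosing regimen". Actual doses are counted from the first Treatment Phase dose "up to and including the last APVO101 dose date on study".

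In the formula for a child on twice weekly throughout, the numerator is the "number of infusions recorded in the subject diary", with no restriction to prophylaxis. The expected period ends at the "date of last dose for prophylaxis". In the changed-frequency version each period ends at the last dose taken in it; term B, for example, runs to the "date of last dose when patient was on 'once weekly' frequency".

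SAP 10.8.1 sets the use: "Compliance will be summarized as continuous variable as well as categorized into" two classes, at least 80% and below 80%. It asks for compliance over the whole study rather than by phase.

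Protocol 4.2.2 lists as a possible withdrawal reason "non-compliance with medication or evaluation schedule with impact on subject risk-to-benefit or on protocol integrity". Protocol 5.7.3 foresees that the schedule may not be followed, including a change to on-demand treatment, and has the reasons recorded.

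**The concern.** The end of the denominator is set by the behaviour being measured. Once a child takes a last prophylaxis dose, no further infusion is expected, however long the child stays on study with prophylaxis still prescribed. This does not fit the stated basis of planned doses in the study, or a report that covers the whole study.

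The two windows also differ. The numerator runs to the last APVO101 dose of any kind and the denominator to the last prophylaxis dose. Infusions given for bleeds after prophylaxis has stopped therefore add to the score with nothing added to the expected count.

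At stake is the adherence summary that gives context to a prophylaxis bleeding rate. Protocol 3.3 aims for 15 to 20 evaluable children, 10 per age group, so one misplaced child visibly shifts the ≥80% share.

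**Working it through.** The documents state no compliance result, so there is no figure to reproduce. The stop times and gaps below are illustrative assumptions; no document gives them.

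**Formula used.** As bracketed in SAP section 2, the twice-weekly formula multiplies by 2/7 where it should divide: 50 infusions in 175 days gives 100 × (50/175) × 2/7 = 8.2% literally, against 100 × 50/(175 × 2/7) = 100% as intended. The A + B version is correctly formed. I use the intended reading: 100 × N / [(last prophylaxis dose − first dose) × 2/7].

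**Permanent stop after 12 weeks on schedule.** Infusions at 3.5-day spacing over 84 days number 25, counting both ends.
- SAP: 84 × 2/7 = 24 expected; 25/24 = 104.2%, whatever follows.
- Schedule to withdrawal at week 16, 20 or 24, counting both ends: 33, 41 or 49 expected, giving 75.8%, 61.0% or 51.0%.
- Without the extra first dose (32, 40, 48): 78.1%, 62.5%, 52.1%. The class is the same either way.

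**Stop at week 20 of 26.** SAP: 41/40 = 102.5%. Schedule to week 26: 41/53 = 77.4%.

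**Short and long gaps.** Take 26 infusions in 13 weeks, with the last 25 × 3.5 = 87.5 days after the first. The SAP expects 87.5 × 2/7 = 25, so the score is 26/25 = 104.0% in every row.

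| Gap to withdrawal | Expected, 2 per week | Compliance |
|---|---|---|
| 1 week | 28 | 92.9% |
| 2 weeks | 30 | 86.7% |
| 4 weeks | 34 | 76.5% |
| 8 weeks | 42 | 61.9% |

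For w weeks on schedule and a gap of g weeks, w/(w + g) falls below 80% only if g > w/4. At w = 13 that is a gap of more than 3.25 weeks.

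**Misses before the last prophylaxis dose.** Over 26 weeks with the last dose at the end, the expected count is 25.5 × 7 × 2/7 = 51. A child taking 26, 31 or 36 infusions scores 51.0%, 60.8% or 70.6%. A child who stops at week 13 and takes one prophylaxis dose at the end scores 27/51 = 52.9%. Such misses are counted.

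**On-demand infusions after prophylaxis stops at week 13.** With 3, 6 or 12 later infusions in the diary, the SAP gives 29/25 = 116%, 32/25 = 128% or 38/25 = 152%. Counting prophylaxis infusions only, the figure is 26/52 = 50% at week 26 if prophylaxis was still prescribed, or 26/26 = 100% if the regimen was recorded as ended at week 13.

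**Effect on the class.** One child is 1/20 = 5 points of the ≥80% share, or 1/10 = 10 points in an age group of 10.

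**The case against.** The best defence is that compliance up to the last prophylaxis dose is a coherent on-treatment measure. The primary endpoint is the bleeding rate while on prophylaxis, and SAP 10.7.1 ends its count and its person-time 3 days after the last prophylaxis dose, or earlier if the child left. Compliance and bleeding rate then cover nearly the same period, and persistence is reported elsewhere. SAP 10.4 tabulates completion of the 50 ED and 100 ED visits and reasons for discontinuation. SAP 10.5 summarizes major deviations. SAP 10.8.1 gives exposure-day classes and reasons for regimen changes. The 12-week child above has 26 exposure days including the PK dose, so is missing from the ≥50 ED class.

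This stands as a reason to keep the on-treatment figure. It does not justify labelling that figure as planned doses over the whole study. It also does not explain why the numerator runs past the denominator, and the other tables do not correct a wrong ≥80% class.

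Two further points stand. The size depends on the gap, and short gaps leave the class unchanged. Counting to a bare data cut-off would be wrong in the other direction: diaries are reviewed at visits (Protocol 5.7.3), about every 3 months late in the Continuation Phase (Protocol 6.4), and SAP section 11 plans an interim analysis. Infusions not yet entered would look missed.

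**Conclusion.** The defect is real and limited. A permanent stop of prophylaxis before withdrawal or end of study is not counted as missed doses, and later on-demand infusions can inflate the score. Compliance is therefore overstated for such a child, and so is the ≥80% class when the gap is long enough: a child on schedule until the stop scores just over 100% where the schedule to withdrawal gives 51% to 76% in the 12-week examples. This rests on the intended bracketing, a child on schedule until the stop, prophylaxis still prescribed during the gap, and assumed gap lengths.

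A reader might infer that every child withdrawn for non-compliance is scored as fully compliant. The documents do not support that: doses missed before the last prophylaxis dose stay in the denominator, and Protocol 4.2.2 does not say that such a withdrawal takes the form of a clean stop. Nor is stopping hidden from the report, given the disposition, deviation and exposure-day summaries. The bleeding rate is not affected either: compliance does not enter its formula, and SAP section 9 uses the Safety population for all efficacy analyses.

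**What to change.** In SAP section 2, end the expected-infusion count at the earlier of (a) the recorded end of the prescribed prophylaxis regimen and (b) study completion or withdrawal. For a child still on study at an interim cut, end it at the last date covered by reviewed diary data, not at the data cut-off. Apply the same end date to the last regimen period in A + B. Count only prophylaxis infusions, in that same window. Compliance up to the last prophylaxis dose may be shown alongside, labelled as on-treatment adherence matching the bleeding-rate window.

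The 2/7 bracket can be corrected in the same edit, but doing so does not cure this point.

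The cost is a short SAP change and some programming. Withdrawal dates are documented (Protocol 4.2.2), the end-of-study date is already used in SAP 10.7.1, and regimen data are already listed (SAP 10.8.1). Reported compliance may be slightly lower.

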5.1.2 TREATMENT PHASE

After completion of PK Phase assessments, subjects will be treated with a prophylaxis regimen of APVO101. Subjects will receive a single intravenous (IV) dose of APVO101 twice weekly or at a frequency of infusions as determined appropriate by the investigator for the particular study subject for a total of 50 ED (approximately 6 months). The starting prophylaxis dose will be based on APVO101 recovery from PK Phase assessments (only pre-infusion and 15-30 minute post-infusion samples; ideally within the recommended dose range: 35 – 75 IU/kg, twice weekly).

For treatment and control of breakthrough, spontaneous or trauma-related bleeding episodes, the dose should be based on severity of bleeding episodes; see below:

- Minor bleeding episodes and/or moderate bleeding episodes: 40 – 60 IU/kg;
- Major or life-threatening bleeding episodes: 60 – 100 IU/kg.

During APVO101 prophylaxis treatment and/or APVO101 treatment for control and management of bleeding episodes, every effort will be made to ensure that the prescribed dose per kilogram body weight is given. However, since it may be difficult to determine fractions of a vial for purposes of providing an exact dose, it is acceptable to round up or down to the nearest vial. The process of rounding up or down should not, however, result in the study subject receiving $>120\%$ or $<90\%$ of the prescribed dose. The exact amount of factor IX infused must be recorded.

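### As printed, the SAP's twice-weekly compliance formula leaves 2/7 outside the divisor; coded literally, it would score a fully adherent child at about 8%

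*SAP*

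**What the plan says.** SAP section 2 (Definitions) bases compliance on actual and planned APVO101 doses and says of the planned number: "The number of infusions expected will be calculated for each subject based on their prescribed dosing regimen". It then prints two formulas. (The curly brace in some quoted formula lines is left over from PDF conversion and has no meaning.)

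- **Constant twice-weekly dosing.** This formula is introduced by "If a patient received APVO101 dose twice weekly during whole study compliance will be calculated as following". Its numerator is the "number of infusions recorded in the subject diary". The divisor is a parenthesis holding the last prophylaxis dose date minus the first dose date. The parenthesis closes there and the factor follows it: "date of first dose}) * 2/7". The square bracket encloses the whole expression, numerator included, so it does not tie 2/7 to the days.
- **Twice weekly, then once weekly.** Here the expression is "number of infusions recorded in the subject diary} / (A + B"), where term A for the twice-weekly period is twice the date difference, all over seven: "date of first dose})] / 7". Term B is the once-weekly period in days over seven. Further changes of frequency are also to be handled in the denominator.

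SAP section 10.8.1 says how the result is used: "Compliance will be summarized as continuous variable as well as categorized into" two classes, at least 80% and below 80%. It refers back to section 2 for the derivation and does not restate it. SAP section 12, which lists departures from the protocol's analysis, does not mention compliance.

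**The concern.** For twice-weekly dosing the expected number of infusions is days × 2/7. Compliance is recorded infusions divided by that number. In the printed line, division and multiplication have equal rank and run left to right, so 2/7 multiplies the ratio and is not part of the divisor. The quantity computed is infusions per day times 2/7, which is not a percentage of planned doses.

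Twice weekly is the regimen that both documents name first, so the faulty line covers the default case. At stake is one descriptive table for at most 22 children. Coded as printed, adherent children on a constant schedule would all appear in the below-80% class. Children who changed frequency would be scored on the correct scale in the same table. SAP section 11 takes the section 10 summaries of the safety endpoints into the interim analysis for the US post-marketing report. Exposure and compliance sit under the safety heading, so the same table may be used there.

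**Working it through.** The documents give no compliance percentage, so there is no stated figure to reproduce. The check evaluates the printed formula and compares it with term A.

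**Inputs**

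- n = infusions recorded in the diary (SAP section 2).
- d = last prophylaxis dose date minus first dose date, in days (SAP section 2).
- Planned rate = 2 per 7 days (SAP section 2).
- Cut = 80% (SAP section 10.8.1).
- Example length: SAP section 5.1.2 describes treatment "for the particular study subject for a total of 50 ED (approximately 6 months"). Assumption: even spacing of 3.5 days. Then 50 infusions span 49 intervals, and d = 49 × 3.5 = 171.5 days.

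**Formulas**

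- As printed: 100 × (n / d) × 2/7.
- With 2/7 in the divisor: 100 × n / (d × 2/7). This equals 100 × n / A, because A = 2d / 7.
- Ratio of the second to the first: (7/2)² = 12.25, whatever n and d are.

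**Fully adherent twice-weekly child**

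| Infusions n | Days d | As printed | 2/7 in divisor |
|---|---|---|---|
| 5 | 14 | 10.2% | 125% |
| 50 | 171.5 | 8.3% | 102.0% |
| 52 | 182 | 8.16% | 100.0% |
| 100 | 346.5 | 8.25% | 101.0% |
| 200 | 696.5 | 8.20% | 100.5% |

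For the second row: 50 / 171.5 × 2/7 = 0.0833, against 50 / 49 = 1.020. With longer follow-up the printed version tends to (2/7)² = 8.16%. Very short follow-up raises it only a little. Two infusions three days apart give 2/3 × 2/7 = 19.0%, the highest value found for an adherent schedule.

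**Can the printed formula reach 80%?** It needs n / d = 0.8 × 7/2 = 2.8 infusions per day, or 19.6 per week, which is 9.8 times the plan. Even daily infusion scores only 2/7 = 28.6%.

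**Child who changes frequency.** Take 182 days twice weekly and then 182 days once weekly, with full adherence: n = 52 + 26 = 78, A = 2 × 182 / 7 = 52, B = 182 / 7 = 26, and compliance = 78 / 78 = 100%. The first 182 days alone, scored by the printed constant-schedule line, give 8.16%. The two rules therefore disagree about the same period of dosing.

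**Does the cut work after correction?** Over 171.5 days, 39 infusions give 39 / 49 = 79.6% and 40 give 40 / 49 = 81.6%, so the 80% cut separates them. As printed, the same children score 6.5% and 6.7%.

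**The case against.** The strongest reply is that the SAP already settles the meaning. The prose defines compliance by expected infusions, and term A shows where the factor goes. Read together, they allow only infusions / (days × 2/7). A SAP formula must be translated into code, and a programmer would probably supply the bracket. A column of values near 8% beside others near 100% would be hard to miss. Compliance is descriptive, and the by-subject listings of doses and regimens in section 10.8.1 would let anyone recompute it. All of this stands. It makes the consequence conditional, but it does not make the printed line right. A literal program gives a meaningless table, and a silently corrected one departs from the SAP.

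A formula's layout can also be lost when text is taken from a PDF, for instance if it was set as a stacked fraction. The brackets of the neighbouring formula came through coherently, so this is a caution only. A look at the typeset page will settle it.

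A reader might infer two stronger things that the documents do not support:

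- **That the trial will report compliance of about 8%.** The documents do not show how the line is programmed. The table shells are in a separate document (SAP section 14).
- **That the reading of the annualized bleeding rate is compromised.** SAP section 10.7.1 computes that rate from bleeding episodes and dates, with no compliance term. Section 9 uses the Safety population for all efficacy and safety analyses and defines no compliance-based set. Protocol section 1.2.2 mentions compliant regimens only as background on an earlier study.

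**Conclusion.** The printed formula for constant twice-weekly dosing is wrong and contradicts the formula beside it. Implemented literally, it is too low by a factor of 12.25, gives a fully adherent child about 8%, and puts every such child below the 80% cut. The A + B formula scores children who changed frequency near 100%, so the compliance table would mix two scales. The damage is confined to that descriptive table; the annualized bleeding rate and the safety endpoints are untouched.

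The factor of 12.25 needs no assumption beyond ordinary left-to-right evaluation and the brackets being as printed. The worked percentages also assume even 3.5-day spacing and full adherence.

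**What to change.** In SAP section 2 and in the programming specification, write: Compliance % = 100 × number of infusions / [(date of last prophylaxis dose − date of first dose) × 2/7]. This matches term A.

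The cost is one pair of brackets. No data collection, dosing or clinical rule changes. If programming has started, check that the code for constant-schedule children uses this divisor.

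A small excess over 100% remains after the correction, because n doses span n − 1 intervals: 2.0 percentage points at 50 infusions and 1.0 at 100. That is a separate matter, and a table footnote would cover it. In the 171.5-day example it does not change the class: against 50 planned doses, 39 give 78.0% and 40 give 80.0%, on the same sides of the cut as 79.6% and 81.6%.

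### When a child's dosing frequency changes, the compliance denominator omits the time between the last dose on the old schedule and the first on the new, so a break at the switch never lowers compliance

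*SAP*

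**What the plan says.** SAP section 2 (Definitions, Compliance) begins with a principle: "The number of infusions expected will be calculated for each subject based on their prescribed dosing regimen". It then gives formulas.

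- **One schedule throughout.** The infusions recorded are compared with a single span, from the first dose to the "date of last dose for prophylaxis", at two per week.
- **Twice weekly, then once weekly.** The numerator is the "number of infusions recorded in the subject diary" and the denominator is A + B. A is twice the number of weeks from the first dose to the "date of last dose when patient was on 'twice weekly' frequency". B is the number of weeks from the "date of first dose when patient was on 'once weekly' frequency" to the last once-weekly dose.
- **More than one change.** The same construction is extended, "taking into account all periods of different dose frequencies in the denominator".

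SAP section 10.8.1 sets the reporting: "Compliance will be summarized as continuous variable as well as categorized into" 80% or more and below 80%, over the whole study. Protocol section 5.7.2 lets the investigator change the infusion frequency, so the switch formula can come into use.

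**The concern.** A and B are bounded by doses actually given. A closes with the last dose on the old schedule and B opens with the first on the new one. Days between those two doses add to neither, and no infusion is expected in them. Each further change of frequency drops another such interval.

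Two children with the same break in prophylaxis are therefore scored differently. If the break falls inside one schedule, it lengthens the span and lowers compliance. If it falls at a change of schedule, it disappears. Both children enter the same continuous summary and the same 80% split. At stake is whether the compliance table means the same thing for every child, and whether it follows the SAP's own rule about the prescribed regimen.

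**Working it through.** The documents state no numerical compliance result, so there is no figure to reproduce. The check applies the SAP formulas to assumed dose calendars with no missed dose inside either period, and varies only the gap at the switch.

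**Formula (SAP section 2).** Compliance = 100 × N / (A + B), with A = 2 × (last twice-weekly dose − first dose)/7 and B = (last once-weekly dose − first once-weekly dose)/7, dates in days. The gap g between the two periods does not appear, so changing g cannot change the result.

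**Main example (assumed).** 51 twice-weekly infusions over 175 days, then 25 once-weekly infusions over 24 weeks.

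- N = 51 + 25 = 76
- A = 2 × 175/7 = 50
- B = 24
- SAP value: 76/74 = 102.7%, for every g

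Now add only the gap to the denominator. The bounds are one expected infusion per week (new frequency throughout the gap) and two per week (old frequency throughout).

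| Gap | SAP | Gap at once weekly | Gap at twice weekly |
|---|---|---|---|
| 1 week | 102.7% | 76/75 = 101.3% | 76/76 = 100% |
| 4 weeks | 102.7% | 76/78 = 97.4% | 76/82 = 92.7% |
| 8 weeks | 102.7% | 76/82 = 92.7% | 76/90 = 84.4% |

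The overstatement is 1.4 to 2.7 points at 1 week, 5.3 to 10.0 at 4 weeks and 10.0 to 18.3 at 8 weeks. If the prescribed change falls h weeks into a gap of g weeks, the denominator is 74 + 2h + (g − h), which lies between the two bounds.

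**Shorter follow-up (assumed).** 26 twice-weekly infusions at alternating 3- and 4-day intervals (87 days), then 13 once-weekly infusions: N = 39, A = 2 × 87/7 = 24.86, B = 12.

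- SAP value: 39/36.86 = 105.8%, for every g
- 8-week gap: 39/44.86 = 86.9% at once weekly; 39/52.86 = 73.8% at twice weekly
- 12-week gap: 39/48.86 = 79.8% at once weekly; 39/60.86 = 64.1% at twice weekly

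Here the 80% category can change.

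**Same break inside one schedule (assumed).** 51 twice-weekly infusions with one break after the 26th, reading the one-schedule denominator as days × 2/7.

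- No break: 175 days, 51/50 = 102.0%
- 28-day break: 199 days, 51/56.86 = 89.7%
- 56-day break: 227 days, 51/64.86 = 78.6%

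A 56-day break inside one schedule takes this child below 80%. A 56-day break at a switch leaves the SAP value unchanged.

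Values above 100% without a break have a separate cause: n doses are divided by n − 1 intervals. The comparisons above leave that uncorrected, so they show the gap alone.

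**The case against.** Most of the case on the other side concerns how much follows from the formula.

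- **Not every gap is missed treatment.** If the investigator paused dosing before the new schedule, nothing was prescribed and nothing should be expected. This stands. The answer is to treat a prescribed pause explicitly, since the present formula drops prescribed and unprescribed breaks alike.
- **The gap would be seen elsewhere.** SAP section 10.8.1 lists treatment administration by subject and dose-regimen data with reasons for changes, and Protocol section 5.7.3 has departures from the schedule documented. With at most 22 children, a break of several weeks would show in the listings. This limits the harm but does not correct the summary statistic.
- **The 80% category often survives.** In the main example even an 8-week gap leaves the child above 80%. Crossing it takes shorter follow-up or a longer gap, and all of these are assumed scenarios.

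Two stronger readings are tempting. A reader might infer that children who change frequency are those whose prophylaxis was failing, so that the error falls on the worst adherers. The documents do not say so: frequency set by the investigator is part of the planned regimen (Protocol section 5.7.1), section 5.7.2 names many determinants including factor IX activity, and the SAP's example is a reduction in frequency, which may equally follow good control. A reader might also infer that the compliance table is the key to interpreting the ABR. No section makes that link: efficacy is analysed in the Safety population, and neither an analysis set nor a sensitivity analysis depends on compliance.

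**Conclusion.** The defect holds as a matter of the SAP's text. For a child whose frequency changes, the written formula gives the same compliance whatever the break at the switch, contrary to the SAP's stated principle and unlike its treatment of a child on one schedule. In the main example this overstates compliance by 5.3 to 10.0 points for a 4-week gap and 10.0 to 18.3 points for an 8-week gap, depending on which frequency applies during the gap. These figures rest on assumed calendars with no other missed doses and no prescribed pause.

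The consequence is small. Only children who change frequency are affected, and their number is not stated. An ordinary interval of about a week moves the result by 1.4 to 2.7 points in the main example. Compliance is descriptive, and the ABR calculation is unchanged. One ambiguity remains: the SAP does not say whether an infusion given to treat a bleed during the break counts as the last dose on the old schedule. If it does, A extends to that infusion and part of the gap is recovered.

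**What to change.** In SAP section 2, replace A and B with contiguous regimen periods:

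- The first period starts at the first Treatment Phase dose.
- Each period ends, and the next begins, on the recorded date on which the prescribed frequency changed. It should not be the date of the first dose given on the new schedule, because ending one period at the recorded change and starting the next at its first dose would reopen the hole.
- The last period ends at the last prophylaxis dose.
- Expected infusions are the sum over periods of days × prescribed frequency. A pause prescribed by the investigator is its own period with zero expected infusions.

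The correction for n doses against n − 1 intervals is a separate decision. If adopted, it should apply to all children, including those on one schedule.

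The cost is a few lines of SAP wording and a small programming change before database lock. Dose-regimen data and reasons for changes are already planned for listing. The sponsor should confirm that the date of each prescribed change is among the data captured, since the SAP does not say so expressly.
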